**Clinical study #5 . Post op-trabeculectomy. DexNP (Gottfredsdottir et al. 2016).**  
**15 patients treated with DexNP**

In a study of DexNP for trabeculectomy (Gottfredsdottir et al., 2016, manuscript in preparation) 15 patients received DexNP 6 times a day for 4 weeks followed by 4 times a day for 2 weeks and 2 times a day for 2 weeks, 8 weeks in all. No serious adverse effects were noted. The group that was treated for 8 weeks with DexNP a day had similar IOP and visual acuity as the 10 patient control group treated with mitomycin C and Maxidex(R) 4 times a day for 8 weeks. No infections, corneal damage or other adverse effects were seen in this study.

**Clinical study #6 Post op-trabeculectomy. DexNP (Jóhannesson et al. 2014). 6 patients treated with DexNP**

Six subjects received one DexNP eye drop in one eye. The peak concentration ( $\mu\text{g/mL} \pm \text{standard deviation}$ ) of dexamethasone for DexNP eye drops ( $636.6 \pm 399.1$ ) was up to 19-fold higher than with Maxidex® ( $39.3 \pm 18.9$ ) ( $p < 0.001$ ). At 4 hrs, DexNP was still 10 times higher than Maxidex®. In addition, DexNP resulted in about 30-fold higher concentration of dissolved dexamethasone in the tear fluid of extended time period allowing more drug to partition into the eye tissue. No adverse effects were noted.

**Clinical study #7 PK with cataract surgery. Dexamethasone cyclodextrin eye drops (Kristinsson et al. 1996) ; 91 patients treated with dexamethasone cyclodextrin eye drops**

Using an earlier preparation for 0.3 and 0.7% dexamethasone hydroxypropyl- $\beta$ -cyclodextrin eye drop preparation, (Kristinsson et al. 1996) applied one eye drop to 91 patients before cataract surgery and measured dexamethasone concentration in aqueous humor. No adverse effects were reported.

**Clinical study #8 Post op-cataract. Dexamethasone cyclodextrin eye drops (Saari et al. 2006); 10 patients treated with dexamethasone cyclodextrin eye drops**

Saari applied a 0.7% dexamethasone, 2-hydroxypropyl- $\beta$ -cyclodextrin eye drop once a day for 3 weeks to patients following cataract surgery. All patients fared well and no adverse effects were reported.

### **Safety profile**

The side effects of corticosteroids in the eye are well known and include cataract formation, increased intraocular pressure and increased risk of infections. During the relatively short duration of treatment in our trials, 4-12 weeks, we did not identify noticeable cataract formation on slitlamp examination and no visual impairment due to cataract.

The intraocular pressure rose modestly during the Tanito study (Tanito et al. 2011) and only one patient had an increase as high as 8 mmHg. This regressed following cessation of treatment and no patient needed treatment for increased intraocular pressure. The Ohira study (Ohira et al. 2015) that went on for 16 weeks (DexNP treatment for 12 weeks) also showed only modest IOP rise. Again, in a longer term study increased intraocular pressure may be more prevalent, but cessation of the DexNP eye drops has been shown to lead to a reduction in IOP to baseline values. We saw no infections in this clinical trial or other adverse events. Side effects of cyclodextrin in this formulation have not been seen and are unlikely.

Cyclodextrins can be found in several marketed eye drops as well as parenteral solutions. (Loftsson & Brewster 2010)  $\gamma$ -Cyclodextrin, the cyclodextrin used in this study, has GRAS (generally regarded as safe) status (<http://www.accessdata.fda.gov/scripts/fcn/fcnDetailNavigation.cfm?rpt=grasListing&id=46>) and can also be found in FDA's list of inactive pharmaceutical ingredients (<http://www.accessdata.fda.gov/scripts/cder/iig/>, search word "cyclodextrin").

$\gamma$ -Cyclodextrin, unlike  $\alpha$ - and  $\beta$ -cyclodextrin, is rapidly digested by salivary and pancreatic  $\alpha$ -amylase (Munro et al. 2004) and indeed the degradation is started by  $\alpha$ -amylase in the tear fluid. Our group has tested several cyclodextrin containing eye drops

in human subjects without any significant adverse effects. (Kristinsson et al. 1996; Gudmundsdóttir et al. 2000; Saari et al. 2006) The possibility of treating diabetic macular edema with noninvasive topical eye drops is a good option for patients and doctors alike. The effectiveness of the drug delivery platform in diabetic macular edema also suggests that it may be useful for other retinal and intraocular diseases, also with other drug molecules.

#### **Summary of human use:**

To summarize the human use of DexNP eye drops, they have been used in 19 patients for 4 weeks 3 to 6 times a day (Tanito et al. 2011); 12 patients for 12 weeks 3, 2 and 1 times a day (Ohira et al. 2015), 8 eyes in 5 patients for 8 weeks, 4 times a day with taper (Shulman et al. 2015), 3 patients for one month 4 times a day (Krag & Hessellund 2014), 15 patients 6 to 2 times a day for 8 weeks (Gottfredsdottir et al. 2016). Jóhannesson (Jóhannesson et al. 2014) gave DexNP to 6 patients. This is 60 patients treated for up to 12 weeks with up to 6 times a day frequency. No serious adverse effects have been noted.

In addition 101 patients received an earlier dexamethasone cyclodextrin eye drops either once or once a day for 3 weeks with no adverse effects.

The effectiveness by the dexamethasone cyclodextrin nanoparticle eye drops in clinical trials is promising. The dexamethasone cyclodextrin nanoparticle eye drops may have a role as monotherapy, and also in combination with intravitreal injections, implants and laser treatment.

Additional information regarding the study treatment is available in the Investigators Brochure.

## **2 STUDY OBJECTIVES**

1. Compare the effects of DexNP eye drops and eye drops containing vehicle on visual acuity and central macular thickness in patients with DME over 12 weeks.
2. Monitor safety of the DexNP eye drop suspension treatment over 12 weeks.

## **3 CLINICAL HYPOTHESES**

1. Proprietary DexNP eye drops improve visual acuity and decrease central macular thickness significantly more than vehicle in patients with DME.
2. Proprietary DexNP eye drop formulation is safe and well tolerated.

## 4 OVERALL STUDY DESIGN

Multi-center

Double-masked

Parallel group

Randomized (2: 1; active: vehicle)

Vehicle controlled

Prospective

12 weeks active treatment, 4 weeks safety follow-up without treatment

1 drop three times a day

## 5 STUDY POPULATION

### 5.1 Number of Subjects (approximate)

Based on 80% power, it was estimated that 96 randomized patients are needed, 64 in the DexNP arm and 32 in the vehicle arm.

Approximately 13 sites will be included, expected number of patients recruited per site per months is 2-5. Sites can enroll more patients if feasible, the recruitment will be competitive, i.e. the enrolment will be stopped once all planned 96 patients are recruited.

### 5.2 Study Population Characteristics

Diabetic macular edema of less than 3 years duration since diagnosis with VA 73-24 ETDRS letters, i.e. 20/40 to 20/320.

Patients who are diagnosed with DME will be approached by ophthalmologists in their clinics. They will be informed about the study and if willing to participate, they will be asked to read and sign an informed consent form.

Participants will undergo a complete eye examination and fill out a questionnaire on medical and eye health, drug use and allergies.

Once a study subject has signed informed consent, he/she will be randomized to active treatment or vehicle.

### 5.3 Inclusion Criteria

**Each subject must:**

- a) Have DME of less than 3 years duration since diagnosis with presence of intraretinal and/or subretinal fluid in the study eye, with central

- macular thickness, CMT, of  $\geq 310\mu\text{m}$  by SD-OCT at baseline (Visit 2) (as measured by the Investigator).
- b) Have definite retinal thickening in the study eye due to DME involving the central macula based on the Investigator's clinical evaluation and by SD-OCT; Note: If the DME consists of circumscribed, focal leakage that the evaluating Investigator believes should be treated with laser and no other treatments, the eye is not eligible to be a study eye.
  - c) Have an ETDRS BCVA letter score  $\leq 73$  (Snellen 20/40) and  $\geq 24$  (Snellen 20/320) in the study eye at baseline (Visit 2)
  - d) Have a documented diagnosis of type 1 or type 2 diabetes mellitus and a glycosylated hemoglobin A1c (HbA1c) of  $\leq 12.0\%$  at Visit 1
  - e) Have a negative urine pregnancy test at Visit 1, if female of childbearing potential those who have experienced menarche and who are not surgically sterilized [bilateral tubal ligation, hysterectomy or bilateral oophorectomy] or post-menopausal [12 months after last menses] and must use adequate birth control throughout the study period. Adequate birth control is defined as hormonal – oral, implantable, injectable, or transdermal contraceptives; mechanical – spermicide in conjunction with a barrier such as condom or diaphragm; intrauterine device (IUD); or surgical sterilization of partner. For non- sexually active females, abstinence may be regarded as an adequate method of birth control;
  - f) Agree to not participate in another interventional study after providing informed consent and until the study is completed
  - g) Provide written informed consent prior to any study procedure being performed and be able and willing to follow all instructions and attend all study visits
  - h) Be 18-85 years of age at baseline (Visit 2), of either sex and any race or ethnicity

#### 5.4 Exclusion Criteria

##### Each subject must not:

- i) Have macular edema considered to be due to a cause other than DME; Note: an eye should not be considered eligible if: (1) the macular edema is considered to be related to ocular surgery such as cataract extraction; (2) clinical exam and/or OCT suggest that vitreoretinal interface abnormalities disease (e.g., a taut posterior hyaloid or epiretinal membrane) is the primary cause of the macular edema, or (3) the macular edema is considered to be related to another condition

- such as age-related macular degeneration, uveitis, retinal vein occlusion, or drug toxicity
- j) Have a decrease in BCVA due to causes other than DME (e.g., foveal atrophy, pigment abnormalities, dense subfoveal hard exudates, previous vitreoretinal surgery, central serous retinopathy, non-retinal condition, substantial cataract, macular ischemia) that is likely to be decreasing BCVA by three lines or more (i.e., cataract would be reducing acuity to 20/40 or worse if eye was otherwise normal)
  - k) Have significant macular ischemia, as assessed by the investigator, which in the opinion of the investigator would prevent gain in visual acuity.
  - l) Have any other ocular disease that may cause substantial reduction in BCVA, including, retinal detachment, epiretinal membrane, vitreous hemorrhage or fibrosis involving the macula in the study eye, ocular inflammation (uveitis), other retinal inflammatory or infectious diseases
  - m) Have active peri-ocular or ocular infection (e.g., blepharitis, keratitis, scleritis, or conjunctivitis)
  - n) Have a history of non-infectious uveitis
  - o) Have high myopia (-8 diopter or more correction) in study eye
  - p) Wear contact lenses during the 12 week active treatment study period
  - q) Have a history of any ocular surgery within 3 months prior to Visit 1 in the study eye;
  - r) Have a history of Yttrium-Aluminum-Granate (YAG) laser capsulotomy within 3 months prior to Visit 1 in the study eye;
  - s) Have a history of panretinal scatter photocoagulation (PRP) or focal laser within 3 months prior to Visit 1 or an anticipated need for PRP during the course of the study in the study eye;
  - t) Use other ophthalmic formulations during the study. However, IOP lowering eye drops are allowed if they become necessary due to increased IOP.
  - u) Have a history of prior IVT, subtenon, or periocular, non-sustained release, steroid therapy within 3 months prior to Visit 1 in the study eye (e.g., triamcinolone)
  - v) Have a history of intravitreal sustained release dexamethasone therapy within six months prior to Visit 1 in the study eye;
  - w) Have a history of intravitreal sustained release fluocinolone within three years prior to Visit 1 in the study eye;

- x) Have a history of prior treatment of intravitreal (IVT) aflibercept within 8 weeks and ranibizumab/bevacizumab within 6 weeks of Visit 1 in the study eye;
- y) Have a history of prior treatment for DME with any other (than previously listed) approved treatment which is not labeled for DME within one year prior to Visit 1 in the study eye;
- z) Have high-risk proliferative diabetic retinopathy (PDR), defined in the ETDRS study as at least one of the following:
  - New vessels within one disc diameter of the optic disc (NVD)  $\geq$  1/3 disc area;
  - Any NVD with vitreous or pre-retinal hemorrhage;
  - New vessels elsewhere in the retina (NVE)  $\geq$  1/2 disc area and pre-retinal or vitreous hemorrhage;
- aa) Have uncontrolled ocular hypertension or glaucoma in either eye, defined as intraocular pressure (IOP)  $\geq$  22 mmHg on more than 1 IOP lowering medications at Visit 1
- bb) Have poor media clarity, pupillary constriction (i.e., senile miosis), or lack cooperation that, in the opinion of the evaluating Investigator, would interfere with any study procedures, evaluations, or interpretation of data
- cc) Have any ocular condition that, in the opinion of the Investigator, may require intervention, interfere with evaluations of efficacy or safety or interpretation of data collected in the study
- dd) Have an estimated Glomerular Filtration Rate (eGFR) of  $<$  15mL/min/1.73m^2 as per CKD-EPI equation at Visit 1
- ee) Have a systolic blood pressure  $<$  90 or  $>$  160 mmHg and / or a diastolic blood pressure  $>$  100 mmHg at Visit 1 and 2
- ff) Have a known or suspected hypersensitivity to any components of the test agent
- gg) Be a female subject who is pregnant or lactating or has a positive pregnancy test at Visit 1 or has been pregnant within 6 months before Visit 1 or breast-feeding within 3 months before Visit 1, or planning to become pregnant within 9 months from Visit 1
- hh) Have participated in any interventional clinical study or been treated with any investigational drugs within 30 days or 5 half-lives of the investigational drug, whichever is longer, prior to the initiation of Visit 1
- ii) Have any other condition, which in the opinion of the evaluating Investigator, precludes the subject's participation in the trial

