	

• New vessels elsewhere in the retina (NVE) <math>\geq \frac{1}{2}</math> disc area and pre-retinal or vitreous hemorrhage;

r) Have uncontrolled ocular hypertension or glaucoma in either eye, defined as intraocular pressure (IOP) <math>\geq 22</math> mmHg on more than 1 IOP lowering medications at Visit 1

s) Have poor media clarity, pupillary constriction (i.e., senile miosis), or lack cooperation that, in the opinion of the evaluating Investigator, would interfere with any study procedures, evaluations, or interpretation of data

t) Have any ocular condition that, in the opinion of the Investigator, may require intervention, interfere with evaluations of efficacy or safety or interpretation of data collected in the study

u) Have an estimated Glomerular Filtration Rate (eGFR) of <math>< 15\text{mL/min}/1.73\text{m}^2</math> as per CKD-EPI equation at Visit 1

v) Have a systolic blood pressure <math>< 90</math> or <math>> 160</math> mmHg and / or a diastolic blood pressure <math>> 100</math> mmHg at Visit 1 and 2

w) Have a known or suspected hypersensitivity to any components of the test agent

x) Be a female subject who is pregnant or lactating or has a positive pregnancy test at Visit 1 or has been pregnant within 6 months before Visit 1 or breast-feeding within 3 months before Visit 1, or planning to become pregnant within 9 months from Visit 1

y) Have participated in any interventional clinical study or been treated with any investigational drugs within 30 days or 5 half-lives of the investigational drug, whichever is longer, prior to the initiation of Visit 1

z) Have any other condition, which in the opinion of the evaluating Investigator, precludes the subject's participation in the trial

Study Formulations and Formulation Numbers:	DexNP and DexNP Vehicle
Evaluation Criteria:	
A complete eye examination will be performed.
 

• Visual acuity will be measured on ETDRS chart at 4m with best corrective lenses.

• Intraocular pressure (IOP) will be measured with Goldmann tonometry or I-CARE tonometry (standardized in each center and the same device to be used for a given patient

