#### 8.1.5 Methods for Assignment to Treatment Groups:

At visit 2, the subject will be randomized in a 2:1 ratio to active drug or the vehicle group.

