#### 8.2.2 Escape Medications

If IOP rises above 25 mmHg a topical prostaglandin analog will be considered. If IOP rises above 32 mmHg, the study drug will be discontinued, (DexNP or vehicle eye drops) and the IOP treated with glaucoma drugs or other treatment at the discretion of the study ophthalmologists.

If BCVA drops by 10 letters or more or CMT increases by 20% or more at 2 consequent visits and the changes are judged by the treating physician to be due to DME the patient should be stopped to receive the DexNP or vehicle experimental eye drops and may be treated at the discretion of the investigator with standard of care, i.e. anti VEGF injections or steroid implant. The patient should be asked to return for all scheduled control visits, even if the study drug has been discontinued

If BCVA drops by 10 letters at 2 consequent visits and the decrease in vision is felt by the treating physician to be due to cataract formation the patient shall be offered cataract surgery and IOL implantation. The patient stays in the study and continues with eye drops as indicated by the protocol.

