### 8.3 **Examination Procedures**

#### 8.3.1 Procedures to be performed at Each Study Visit with Regard to Study Objective(s)

A complete eye examination will be performed. (Detailed descriptions may be found in an optional study manual if deemed necessary by the sponsor)

- Visual acuity will be measured at every visit using ETDRS chart at 4m with best corrective lenses.
- Intraocular pressure (IOP) will be measured at every visit with Goldmann tonometry or I-CARE tonometry (standardized in each center and the same device to be used for a given patient throughout the study)
- Eye examined at every visit by slitlamp.
- Fundus is examined at every visit through dilated pupils (i.e. using Tropicamide hydrochloride 1% and phenylephrine 2.5%),
- Fundus photographs obtained (optional)
- Optical coherence tomography (SD OCT preferably using Heidelberg Spectralis) performed at each visit to measure central macular thickness (CMT).
- In phakic eyes cataract formation will be graded using the LOCS III system.
- Irritation will be evaluated at every visit by slit lamp biomicroscopy, fluorescein staining when deemed necessary

- Blood pressure should be measured on the patient sitting for at least 2 minutes, on the right arm.
- Quality of life as assessed by NEI VFQ-25 at baseline and 12 weeks.

The full eye examination will be performed before start of the study at screening and then at each visit (Day 1, weeks 2, 4, 8, 12 and 16) until end of the study period.

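### The IOP exclusion in 5.4(aa) and synopsis (r) sets no numeric limit for an untreated study eye, and no eligibility criterion uses the Visit 2 IOP

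*Combined protocol and SAP*

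**What the plan says.** Section 5.4(aa) excludes uncontrolled ocular hypertension or glaucoma in either eye and defines it by pressure and treatment together: an IOP of at least "22 mmHg on more than 1 IOP lowering medications at Visit 1". Synopsis (r) has the same definition ("mmHg on more than 1 IOP lowering medications at Visit 1").

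Two discretionary criteria could also keep out a high-pressure eye. Section 5.4(cc) covers an ocular condition that, in the investigator's opinion, "may require intervention, interfere with evaluations of efficacy or safety". Section 5.4(ii) is a general clause: "Have any other condition, which in the opinion of the evaluating Investigator" rules out participation. Neither gives a number. Section 5.4(t), which has no counterpart in the synopsis list, and section 8.2 bar other eye drops, with an exception for IOP-lowering drops that become necessary because pressure has risen.

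On timing, 8.3.1 states that "Intraocular pressure (IOP) will be measured at every visit", and Appendix 1 marks IOP at Visits 1 and 2. Under 8.1.5, "At visit 2, the subject will be randomized in a 2:1 ratio".

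For eyes on study, 8.2.2 sets two levels: "If IOP rises above 25 mmHg a topical prostaglandin analog will be considered", and "If IOP rises above 32 mmHg, the study drug will be discontinued".

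**The concern.** The definition in (aa) needs three conditions at once: 22 mmHg or more, more than one drug, and Visit 1. An untreated eye cannot meet the second condition, so (aa) does not exclude it at any pressure. The protocol thus has numeric levels at which a patient on study is considered for treatment or taken off the drug, but no matching level at entry.

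The product is a steroid given three times a day for 12 weeks without a taper. In the 12-patient DME trial in the Introduction, mean IOP rose by 5, 6 and 7 mmHg at weeks 4, 8 and 12, although dosing was tapered to once daily. In the 19-patient trial the mean at week 4 was 17.4 − 15.2 = 2.2 mmHg above baseline. An eye that starts near or above the levels in 8.2.2 has little room for such a rise.

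Screening can precede baseline by up to 28 days, and the reading taken on the day of randomization has no stated role in eligibility. CMT and BCVA are tested at Visit 2, and blood pressure at Visits 1 and 2, so the protocol already makes entry depend on Visit 2 measurements. About 13 sites would have to settle a high IOP by judgement.

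**Working it through.** The plan gives no figure to reproduce here. The check has three parts.

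**1. The rule as written**

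| Study eye | IOP | Excluded by (aa)/(r)? |
|---|---|---|
| No drug | any | No |
| One drug | any | No (5.4(t) and 8.2 may bar it because of the drop, not the pressure) |
| Two or more drugs | below 22 at Visit 1 | No |
| Two or more drugs | 22 or more at Visit 1 | Yes |
| Any | any value at Visit 2 | No |

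The other inclusion and exclusion criteria, in the synopsis and in 5.3 and 5.4, contain no IOP number.

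**2. How many patients**

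Inputs from the Introduction: baseline IOP 14 ± 4 mmHg (12-patient trial) and 15.2 ± 3.1 mmHg (19-patient trial). From 5.1: 96 randomized.

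One visit, normal: p = 1 − Φ((limit − mean)/SD).

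- 14 ± 4, above 25: 1 − Φ(2.75) = 0.00298; × 96 = 0.29.
- 15.2 ± 3.1, above 25: 1 − Φ(3.16) = 0.00079; × 96 = 0.08.
- 14 ± 4, 22 or more: 1 − Φ(2.00) = 0.02275; × 96 = 2.2.
- 15.2 ± 3.1, 22 or more: 1 − Φ(2.19) = 0.01413; × 96 = 1.4.

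Either of two visits: the between-visit correlation is not given, so I take the range from 1 (same p as one visit) to 0, where the probability is 1 − (1 − p)².

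Lognormal with the same mean m and SD s: log-variance v = ln(1 + s²/m²), log-mean ln(m) − v/2. For 14 ± 4 the log-mean is 2.600 and the log-SD 0.280, so above 25: 1 − Φ((ln 25 − 2.600)/0.280) = 1 − Φ(2.21) = 0.01356; × 96 = 1.3.

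| Limit | Distribution | One visit, of 96 | Either visit, maximum (correlation 0), of 96 |
|---|---|---|---|
| above 25 | normal | 0.08 to 0.29 | 0.15 to 0.57 |
| above 25 | lognormal | 0.5 to 1.3 | 1.0 to 2.6 |
| 22 or more | normal | 1.4 to 2.2 | 2.7 to 4.3 |
| 22 or more | lognormal | 2.6 to 3.8 | 5.0 to 7.5 |

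Each range runs over the two earlier trials. Under normality, the either-visit count above 25 mmHg lies between 0.08 (correlation 1) and 0.57 (correlation 0).

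**3. What it means for an affected eye**

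Inputs: rise 5 ± 6 mmHg at week 4 and 7 ± 7 at week 12 (12-patient trial), assumed normal and independent of the entry value. P(IOP above 32) = 1 − Φ((32 − entry − mean rise)/SD).

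| Entry IOP | Week 4 | Week 12 |
|---|---|---|
| 14 | 1.5% | 6% |
| 22 | 20% | 33% |
| 25 | 37% | 50% |
| 26 | 43% | 56% |
| 30 | 69% | 76% |

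For example, entry at 26, week 4: 1 − Φ((32 − 26 − 5)/6) = 1 − Φ(0.17) = 0.43. With 12 patients and a tapered dose behind them, these percentages are illustrative only.

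**The case against.** The best defence is that the protocol already handles this by judgement. Criterion (cc) covers a condition that may need intervention, and an eye at a pressure where 8.2.2 considers treatment fits that description. Randomizing an eye above 32 mmHg would require an ophthalmologist to overlook (cc), (ii) and 8.2.2 together. That largely stands. A reader might infer that such eyes will be enrolled; the documents support only that no number prevents it. What remains is that discretion sets no common limit across about 13 sites.

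Second, 5.4(t) and 8.2 can be read as excluding an eye already on one drop. That is a fair reading, although it sits awkwardly with the more-than-one-drug wording in (aa). It narrows the clear gap to untreated eyes. It sets no pressure limit and does not reach those eyes.

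Third, the Visit 2 reading does have a use. Under 10.6.1 it would normally be the baseline, and so feeds the IOP summaries in 10.6.5. To say it goes unused would be too strong; it is unused for eligibility.

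Fourth, the numbers are small, IOP is checked at every visit, and in the 12-patient trial the mean was only 1 mmHg above baseline four weeks after stopping. In the 19-patient trial no patient needed pressure treatment. All of this stands and keeps the severity low, though monitoring acts only after exposure.

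Fifth, a 25 mmHg cap hardly separates neighbouring eyes: entry at 25 and at 26 carry similar illustrative risks (37% and 43% at week 4). This is true of any cut-off. The case for 25 is consistency with the protocol's own treatment level, not a step in risk.

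**Conclusion.** The gap is real and its effect is small. As written, an untreated study eye is numerically eligible at any IOP, including pressures at which 8.2.2 considers treatment or stops the drug, and only investigator discretion stands in the way.

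The expected count above 25 mmHg at Visit 1 or Visit 2 is about 0.1 to 0.6 of 96 under normality and up to about 2.6 under a lognormal shape. Because eyes at 22 mmHg or more on two or more drugs are already excluded, a reader might take these as upper bounds. The documents do not support that: the figures extrapolate the tails of samples of 12 and 19 patients whose IOP entry rules are not stated. If high pressures were excluded in those trials, the counts here could be too low.

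Nor does the point touch the trial's conclusions on efficacy. Alpha, sample size and the primary BCVA analysis are unaffected. It is a cheap safety improvement.

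**What to change.** Keep the present wording of 5.4(aa) and synopsis (r) and add to both: *or study-eye IOP above 25 mmHg at Visit 1 or Visit 2, regardless of IOP-lowering medication.* The value matches the treatment level in 8.2.2, and both readings are already scheduled.

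The cost is one clause in two places in an amendment, plus the few patients screened out (the counts above 25 mmHg given above). A stricter 22 mmHg limit is a clinical choice for the sponsor. It could screen out up to about 4.3 of 96 under normality or 7.5 under a lognormal shape if either visit counts.
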